## 4) Study Design

We propose a pilot clustered interventional trial with two arms. Clinics in the intervention arm receive Autism ALERT plus an ASD screening intervention (START Autism), and clinics in the comparison intervention (control) arm receive only START Autism (no Autism ALERT). As this is a pilot trial, primary outcomes of interest are feasibility and acceptability. We will additionally assess mechanism of outcome, preliminary efficacy, and protocol fidelity. Feasibility and acceptability will be assessed in intervention clinics. Mechanism of action and preliminary efficacy will be assessed by comparing intervention to control clinics. Fidelity is assessed in both arms. We will pilot test Autism ALERT in 6 safety-net primary care clinics in Oregon: 3 clinics will serve as intervention clinics, receiving both Autism ALERT and START Autism, and 3 clinics will serve as controls receiving START Autism only. Study arm will be assigned via coin-flip randomization of clinics, stratified for size and urbanicity, by a statistician who is not otherwise part of the study team.

In 2023 we received new funding from CareOregon to expand the project. As a result, this pilot study will be expanded to all of Portland-metro area. It will no longer include a control arm. Participants will be recruited off of Autism clinic waiting lists in the PDX metro area, and will be enrolled into the study to receive family navigation services from our partners at Help Me Grow.

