### b) Inclusion and Exclusion Criteria

There are different eligibility requirements for clinics, children/parents, and providers.

To meet eligibility criteria, participating clinics must have >30% Medicaid enrollees or uninsured patients. Family medicine clinics must have >30% children. The study will be initially offered to safety-net primary care practices in 3 Oregon counties. We seek to enroll 6 clinics; if more than 6 clinics initially express interest, we will randomly choose 6 interested clinics, reserving at least two spots for non-metropolitan clinics. If fewer than 6 express interest, we will open recruitment to an additional two counties. Additional counties will be considered if recruitment is inadequate.

Child/parent dyads are eligible for inclusion when the child's PCP suspects the child has ASD. This can be for any reason, including the child having a high-risk ASD screen, or clinical concern. Children with prior ASD diagnoses or prior history of diagnostic evaluation for ASD are excluded. Enrolled children must be between age 12 and 54 months at enrollment to ensure EI/ECSE eligibility.

Provider subjects must be pediatric primary care providers (e.g., physician, nurse practitioner, physician assistant) licensed in Oregon, and must see children age 1-5 for well-child care. Subspecialists are excluded.

For the expansion, any child aged 1-5 years old on an Autism clinic waiting list at OHSU, Randall Children's Hospital, Providence Child Development Institute, Mindsights, or The Children's Program, or a referral from an Autism ALERT trained provider is eligible to join the study, if they have not previously been medically diagnosed with Autism.

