Families will initially receive a study packet from their provider at the time of the referral. The packet will contain a children's book, information about autism, an Early Intervention Referral Form, and a Study Interest Form. Aside from the study interest form and the phone scripts that are used for screening there are no other recruitment materials (e.g., emails, flyers) for family participants at this time. They will learn about the study first from the study interest form. The Study Interest Form will include some general information about the study, as well as a HIPAA authorization allowing disclosure of family contact information and some health information to the study team. The parent will sign the interest form, allowing the clinic to pass the family's contact information to the Navigator team. Navigators will then reach out to the family to complete the online consent process, or phone consent process as necessary (see more information below). Please see Family Consent Form attachments. Family enrollment will be incentivized with a children's book and \$50 stipend per survey completed for both experimental and control groups. Provider participants may receive Continuing Medical Education credits and/or Part IV Maintenance of Certification credits, if desired, as part of their participation in this study. Clinics may also be entered into a raffle to incentivize their patients' referral to the study, based on whether they refer any patients to the study in a given time period. The raffle incentive will be a gift or food basket costing less than \$100. Control arm clinics will also be given a box of chocolate on Valentine's day to further increase enrollment as enrollment is lagging in that arm.

For clinics in the OHSU system, referrals to the Autism diagnostic clinic will also be monitored for potential study recruitment. The diagnostic clinic staff will provide a list of MRNs of patients referred to the OHSU Autism Clinic, which will be transmitted via secure OHSU emails to the referring primary care provider and study team for inclusion in the study. Data will be transmitted as a list of MRNs, which the provider can use EPIC to identify and consider. If the provider gives permission, the study team will directly contact the family. No PHI will leave OHSU.

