##### Providers:

For providers, an IRB-approved information sheet providing all elements of an informed consent will be provided by the study team at the clinic-based training. Providers will be given the option to opt out of the project entirely both initially and subsequently at any point. They do not have to offer the study intervention (Autism ALERT) to any family for whom it may seem inappropriate. Providers will sign a line at the end of the information sheet to indicate their consent; an electronic consent form will also be available for providers who miss the initial project meeting but who still want to participate.

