key document to associate their names with their study IDs, will be sent follow-up emails, and will also be given the option to complete the survey via mail or fax. Paper surveys will be stored securely at OHSU as outlined above and destroyed approximately 6 months after publication of study results. The patient portal survey will be anonymous and no study ID or PHI will be entered. In addition to the survey, chart review data will be collected which contains information about each provider's practice patterns. These data are collected once every 3 months, in both arms. These data include number of children screened for ASD and number of children referred to EI/ECSE for an ASD concern. Note that referrals to Early Intervention are a separate process that is standard of care, and is not related to enrollment in the study. Providers will be encouraged to adhere to standard of care in terms of screening children for autism and referring to Early Intervention; however this process can be accomplished by usual methods without enrolling children in the study if providers prefer. Number of children screened for ASD, and screening test results, will be collected by a practice administrator, using an existing form that we have used in prior research projects. The administrator will be considered engaged in research through an IAA. This form will be encrypted and sent to the study team electronically using OHSU's secure server. Finally, fidelity data (e.g., PCP-Navigator Contact Log) will contain information about interactions between the PCP and the navigator. This file will be kept encrypted and stored on OHSU Box, a secure cloud server.

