## **8) Data Analysis**

Process data from CCMT and Navigator Fidelity Checklist will be used to calculate contact attempts, time to first contact, total time spent per family, and counts of specific navigator activities. Families who complete all calls will be compared to those who broke off contact, and specific points of participant drop-off will be calculated. We will assess whether specific intervention activities varied by family demographic characteristic and clinic site, to assess variability in acceptability, using bivariate analyses. Family survey data will also be used to assess feasibility and acceptability. Initial analyses will focus on families who participated in ALERT, assessing experience of care and improvement suggestions. Next, post-intervention family experience will be compared in intervention vs. control clinics using bivariate analyses with an intention-to-treat approach. We will also examine variation in experience outcomes overall, and by study arm, by demographic characteristics, in order to assess whether the intervention was appropriate for diverse families, and to target improvements. Parent responses to open-ended items will be assessed via conventional content analysis. Using the parent interviews, we will also qualitatively assess families' feelings towards the evaluation process, and for the intervention arm we will also be looking at experiences with family navigators.

PCP process data will be used in a similar fashion. PCP/Navigator interactions will be descriptively characterized, using the PCP-Navigator Con-tact log and use of the PCP Website. PCP survey data will be used to characterize PCPs' post-intervention experiences. PCPs' overall experiences will be compared in both arms using bivariate testing, and open-ended questions will be coded.

We will refine our mechanism hypotheses and measurement by examining change in family-and provider-reported outcomes (e.g., stress, empowerment) pre-and post-intervention, in both study arms, primarily using descriptive and bivariate tests. Exploratory analyses will assess whether mechanism outcomes differ by family race/ethnicity, English proficiency, or insurance type, both overall and by study arm, using bivariate or limited multivariable regression analyses. This will allow us to gather valuable descriptive data on variation in engagement of target mechanisms, which might allow for individualized messaging in future research.

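### Pilot arm contrasts compare families recruited after clinic allocation by PCPs who know their arm, so they are open to selection that an intention-to-treat label does not remove

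*Protocol*

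**What the plan says.** All references are to the Protocol and to its pilot phase.

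- **Allocation (section 4).** "Study arm will be assigned via coin-flip randomization of clinics", stratified by clinic size and by urban or rural location. There are three clinics per arm. Only intervention clinics receive Autism ALERT; both arms receive START Autism.
- **Entry of families (section 5b).** "Child/parent dyads are eligible for inclusion when the child's PCP suspects the child has ASD", whatever the reason for the suspicion.
- **Approach (section 5f).** The PCP hands over the interest form, and the study team then obtains consent. Of PCPs it says: "They do not have to offer the study intervention (Autism ALERT) to any family for whom it may seem inappropriate". Section 6 adds that a PCP may refer to Early Intervention without enrolling the child.
- **Recruitment so far (section 5e).** Control clinics get chocolate "to further increase enrollment as enrollment is lagging in that arm". A raffle is also offered and is not limited to one arm.
- **Second route (section 5e).** For OHSU-system clinics, "referrals to the Autism diagnostic clinic will also be monitored for potential study recruitment". The study team contacts the family if the provider agrees.
- **Analysis (section 8).** "post-intervention family experience will be compared in intervention vs. control clinics using bivariate analyses with an intention-to-treat approach". Efficacy is compared by bivariate methods and Kaplan-Meier curves, and Cohen's d is to inform the next trial. Section 6 limits access to the ecWeb education records to families who have consented.
- **Clinic-level data (section 6).** Chart review is done every three months in both arms: "These data include number of children screened for ASD and number of children referred to EI/ECSE for an ASD concern".

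**The concern.** Randomising clinics makes the clinics, and the eligible children in them, comparable in expectation. It does not do so for the subset who enrol if enrolment happens after allocation and depends on someone who knows the arm. A PCP with a navigation service to offer may bring in different children from a PCP who can offer only a study packet and surveys. They could differ in age, severity or family motivation. Intention-to-treat keeps enrolled families in their clinic's arm, but it does not restore families who were never approached.

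The second route adds to this. A child found through it already has a diagnostic referral, and time from referral to treatment is one of the study's hypotheses (section 2). Six clinics stratified on size and location need not split that route evenly between arms.

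The stake is the family-experience, mechanism and preliminary-efficacy contrasts, and above all the effect size used to plan the next trial. The protocol itself takes this kind of problem seriously: section 5f excludes some language groups partly because small numbers could unbalance the arms.

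**Working it through.** **Step 1: the chain in the text.** Section 4 fixes the arm before any family enters. The arms differ visibly in what the PCP can offer, and no blinding is described, so PCPs know their arm (an inference, but a direct one). Sections 5b, 5f and 6 leave suspicion, offer and enrolment to the PCP. Section 5e reports an enrolment difference by arm. Sections 6 and 8 base the contrast on consenting families and state no adjustment for it.

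**Step 2: what the plan gives in numbers.** Section 5a plans 20 + 25 + 25 = 70 dyads, which adds up. There is no power calculation to reproduce; section 8 says the pilot was deliberately not powered. No enrolment shares by arm are given.

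**Step 3: an illustration of size, with assumed inputs.** Let q be the share of eligible families who enrol. Suppose enrolment selects on a family trait that has correlation r with the outcome. The mean of that trait among enrolees, in SD units, is λ(q) = φ(z₁₋q)/q. The shift in d with no ALERT effect is r × [λ(q_control) − λ(q_intervention)].

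The values are λ(0.8) = 0.350, λ(0.6) = 0.644, λ(0.5) = 0.798, λ(0.4) = 0.966 and λ(0.3) = 1.159.

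| Enrolled share, intervention vs control | r = 0.2 | r = 0.4 | r = 0.6 |
|---|---|---|---|
| 50% vs 50% | 0 | 0 | 0 |
| 50% vs 40% | 0.03 | 0.07 | 0.10 |
| 80% vs 50% | 0.09 | 0.18 | 0.27 |
| 60% vs 30% | 0.10 | 0.21 | 0.31 |
| 80% vs 30% | 0.16 | 0.32 | 0.49 |

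The sign depends on which trait is selected. The zero row also needs the same selection rule in both arms; equal shares reached by different rules can still bias the contrast. Lagging enrolment may also mean fewer eligible children rather than a lower enrolled share, and the protocol does not say which.

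**Step 4: scale.** The SE of d at 25 per arm is about √(2/25) = 0.28. With an assumed intraclass correlation of 0.05 and 25/3 ≈ 8.3 families per clinic, the design effect is 1 + 7.33 × 0.05 = 1.37, and the SE is √(0.08 × 1.37) = 0.33. Most scenarios fall below or near one SE; the most unequal one exceeds it.

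**Step 5: effect on the next trial.** Required sample size goes as 1/d². If the true d were 0.4 (assumed) and selection moved it to 0.5, the next trial would be sized at (0.4/0.5)² = 64% of its need. If selection moved it to 0.3, the figure would be (0.4/0.3)² = 178%.

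**The case against.** The strongest reply is that little hangs on the contrast. The pilot is unpowered, its primary outcomes are assessed in intervention clinics, and the 2023 expansion has no control arm. This stands, and it limits the weight of the point. It does not dispose of it, because section 8 still plans the contrasts and carries Cohen's d forward.

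A second reply is that baseline tables and adjusted analyses are usual SAP content. Their absence alone would be no finding. The point rests on what section 8 does state: a bivariate comparison, for family experience under an intention-to-treat label. That label is not applied to efficacy, where the selection problem is the same.

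A third reply is that the chart-review counts are not a true denominator. That is correct. They are de-identified, they count EI/ECSE referrals rather than children meeting the section 5b criteria, and children from the diagnostic-clinic list need not be among them. Section 8 also treats referral behaviour as something the arms may change. The counts are useful only as an approximate, labelled reference.

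Two stronger readings are tempting:

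- **That the chocolate inflates PCP uptake.** It goes only to control clinics, and feasibility is assessed in intervention clinics, so it cannot. Only the raffle and the diagnostic-clinic list could raise that figure.
- **That equal incentives in both arms are plainly required.** If control enrolment lags, a control-only incentive may bring the enrolled shares closer and reduce the bias in the model above. The choice is open to debate.

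**Conclusion.** The point holds for the pilot's secondary arm contrasts. Recruitment follows allocation, is led by PCPs who know their arm, and is reported to be unequal. An unadjusted comparison of those who consented is therefore open to differential selection.

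A reader might infer that the arms are shown to differ in case mix, or that a particular bias has been established. The documents support neither: they report unequal enrolment, not unequal families. The range of 0.03 to 0.49 SD rests wholly on assumed enrolment shares and correlations and on one selection model, and the true shift could be zero or of either sign. The primary feasibility and acceptability outcomes are not affected by this contrast. The change is worth making because it is cheap and because the effect size will be reused.

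**What to change.** 1. In section 8, describe the family-experience, mechanism and efficacy contrasts as comparisons among enrolled families.
2. Beside the bivariate arm comparison and Cohen's d, report an analysis adjusted for child age at enrolment, with a table of baseline case mix by arm. Adjustment addresses measured differences only, and the text should say so.
3. Record each child's recruitment route (PCP hand-out or diagnostic-clinic list). When describing PCP uptake, report PCP-initiated referrals separately.
4. Report enrolled children by clinic and arm against the three-monthly chart-review count of ASD-concern EI/ECSE referrals, labelled as an approximate denominator that the arm may itself affect.

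Section 6 draws on data already collected from participating pediatricians, so pilot recruitment may be largely complete. Items 1, 2 and 4 can still be done at analysis; item 3 may need the route to be recovered from study records.

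The cost is a little more analysis, one data field, some loss of precision from adjustment at about 25 dyads per arm, and possibly a lower reported PCP uptake.

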#### **f) Consent Process**

There are two informed consent processes in this study: one for primary care providers, and one for children and their parents.

##### Providers:

For providers, an IRB-approved information sheet providing all elements of an informed consent will be provided by the study team at the clinic-based training. Providers will be given the option to opt out of the project entirely both initially and subsequently at any point. They do not have to offer the study intervention (Autism ALERT) to any family for whom it may seem inappropriate. Providers will sign a line at the end of the information sheet to indicate their consent; an electronic consent form will also be available for providers who miss the initial project meeting but who still want to participate.

##### Families:

The consent process for families (in the intervention and control groups) was different than that for primary care providers. Families for whom ASD is suspected will be handed a study interest form by their PCP. The PCP will ask if they are interested in learning more about the study. If so, they will indicate their interest by completing a study interest form. This study interest form will serve as authorization to allow the PCP to release information to the researchers for recruitment purposes. This signed interest form signifies study interest but is not a consent for the study. Interested parents will then be contacted by the study team via phone, text or email, to secure electronic signed consent or verbal consent.

Text messaging, using the secure Twilio app hosted by OHSU, will be utilized for scheduling phone calls. Text messaging will not be used to obtain consent but will be used to schedule a phone appointment to obtain consent. After consenting, the family may also choose to receive text messages from the navigator or study team with updates, reminders, or other scheduling requests.

**Electronic consent:** Families will sign consent electronically through a form built in Research Electronic Data Capture (REDCap). The software allows consent forms to be emailed directly to the email address that the participant provides upon signing the Study Interest Form. Per OHSU OCTRI requirements, participants will click a radio-box for yes or no, and if yes is selected, will enter their first and last name. This will be used in conjunction with the timestamp on the REDCap form to confirm consent to the study. In most cases, participants will provide electronic consent while on the phone with a Navigator, who will be able to confirm their identity through phone, email, and signature congruency.

**Verbal Consent over the Phone:** For families lacking internet access, a verbal consent via telephone will be provided in lieu of electronic signed consent. For these families we have requested a HIPAA waiver/alteration.

**Family consent for Expansion:** Children who are referred from their primary care providers will follow the same consent process as the pilot project, wherein a team member will reach out to them to receive electronic or verbal consent. We will request a HIPAA waiver to reach out to children on the OHSU CDRC, Providence Health Systems, and Legacy Health, Mindsights, and The Children's Program waitlists. This will allow us to contact families off the waitlist and ensure all families have the option of receiving a family navigator, as it is impractical to recruit every single primary care clinic in the Portland metro area to provide referrals to us.

**In the pilot study - Medical record review:** One member of the administrative staff of each participating clinic will be engaged in research, and will complete an IIA in addition to a specialized training on IRB and study procedures (see attachment). (This medical record review process will not be continued in the expansion) They will perform medical record review for each clinic to ascertain autism and developmental screening rates throughout the project. This person will have access to patient medical records as part of their usual work. The administrator will transmit de-identified medical record review information on PCP screening rates and referral patterns using the Medical Chart Review Tool to the study team via fax or secure email.. For this portion of the research, no identifiable patient information will be collected or relayed to the study team. Since no individual identifiers will be collected or transmitted, this portion of the study would not be considered human subjects research. It is not possible to obtain parent consent for this variety of work since thousands of children would be seen in pediatric practices during this time period (in our prior research study of similar design, it was >2000 visits over 6 months). Obtaining consent from this volume of patients in the pediatric office setting would make this project impossible to conduct, since no community pediatric practices would agree to participate. It is also

unnecessary because we are not getting any information that would readily identify individuals based on this chart data we obtain from the clinics.

The research team will repeatedly emphasize to community providers and study team members that participation is optional, and that families should not be coerced to participate. Given that many families of children at risk for autism have low literacy and/or limited English proficiency, all study materials including consent documents will be available at a 6th grade reading level in English and Spanish, and a study research assistant and family navigator will speak both languages fluently. Families speaking languages other than Spanish or English cannot enroll in the study but can be referred to Swindell's existing family navigation services (not part of the research study) if PCPs choose. We cannot enroll non-English/non-Spanish speakers in the study, because from a scientific standpoint their resource use would be quite different. In addition, the low numbers of enrollees in this group might create imbalances in the intervention and control arms that would make data interpretation challenging.

Pregnant women are only enrolled incidentally as part of the general parent study population; no study procedures will entail any risk to pregnant women or their fetuses. This project will not enroll human fetuses, neonates, or prisoners.

